Patients will be randomized into either SIFI block or sham group with an online randomization program by the study PI ([name]) prior to any patient enrollment. Patients will be given a number (1-40), and the randomized numbers will be given to key study personnel member that will be unblinded. The intervention drug, either 30mL 0.2% ropivacaine or sham block, consisting of 30mL saline, will be drawn up by this key personnel member of the study team who is unblinded and will not be involved in the SIFI block or post-operative analysis. This person will supply the regional anesthesiologist with the intervention, however, both the regional anesthesiologist performing the block and the patient will be blind as to the contents of the syringe.

At the completion of the intervention, verbally reported pain scores (NRS 11) and opioid consumption (IV morphine equivalents) will be measured by a blinded observer starting at time zero and monitored every 10 minutes for 1 hour (+/- 5 minutes). Verbal pain scores will then be recorded each hour for first 4 hours, 6 hours and 24 hours (+/- 10 minutes). Patients will have post-operative orders for supplementary pain control that

include 25mcg IV fentanyl for pain scores 5-7 and 50mcg IV fentanyl for pain scores 8-10.

Subjects' verbal pain scores and opioid consumption will be recorded hourly for the first four hours, at 6 hours, and at 24 hours. Dynamometry will be utilized 2 hours post intervention on POD0 to determine the extent of quadriceps weakness achieved by SIFI injection as compared to unblocked leg. Ambulation distance in feet will be measured POD0 and POD1 by physical therapy. These results will be recorded as will hospital length of stay.

5. Selection of Subjects:

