ASA 1-3 patients aged 18-75 years old undergoing primary hip arthroplasty will be enrolled. Patients will be identified preoperatively in either preoperative screening clinic or the night prior to surgery depending on method of preoperative screening. Patients in the study will be ASA 1-3 patients, many will be screened by phone instead of a clinic visit. Patients not seen in preoperative screening clinic will be contacted by telephone by primary investigator ([name]) to confirm eligibility and, if eligible and interested, the study will be explained. Patients will be given the opportunity to ask initial questions about the study over the phone. Patients interested in participating will be again have the protocol fully explained and written informed consent will be obtained on the day of surgery prior to receiving any sedation

Inclusion

Patients that will be included in the study are English speaking 18-75 year old ASA 1-3 patients undergoing primary total hip arthroplasty.

Exclusion

Patients will be excluded from the study if they meet one or more of the following Criteria:

- 1) ASA 4 or 5
- 2) Revision hip arthroplasty
- 3) Diagnosis of chronic pain
- 4) Daily chronic opioid use (over 3 months of continuous opioid use).
- 5) Inability to communicate pain scores or need for analgesia.
- 6) Acute hip fracture
- 7) Infection at the site of block placement
- 8) Age under 18 years old or greater than 75 years old
- 9) Pregnant women (as determined by standard of care day-of surgery urine bHCG)
- 10) Intolerance/allergy to local anesthetics
- 11) Weight <50 kg
- 12) Suspected or known addiction to or abuse of illicit drug(s), prescription medicine(s), or alcohol within the past 2 years.
- 13) Uncontrolled anxiety, schizophrenia, or other psychiatric disorder that, in the opinion of the investigator, may interfere with study assessments or compliance.
- 14) Current or historical evidence of any clinically significant disease or condition that, in the opinion of the investigator, may increase the risk of surgery or complicate the subject's postoperative course.

6. Subject Recruitment & Compensation:

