Only patients who are having total hip arthroplasty are eligible for this study. We will not bias any demographic groups in identifying patients eligible for this study. A total of 40 patients will be consented from Duke University Medical Center. An IRB approved phone script may be used to discuss the study with eligible patients missed at their Pre-Op screening visit. Patients will not receive any additional compensation for enrollment in this study.

7. Consent Process

A patient's permission to be approached for research will be obtained by the primary care team involved with the patient. The consent process will be conducted by the research personnel or one of the physicians involved in the study. The consent process will take place in the pre-operative screening or the surgical clinics. Throughout the consent process, measures will be taken to maintain privacy, such as by conducting face-to-face conversations in private rooms. As much time as necessary will be spent with each potential subject to sufficiently explain and answer all questions, and address all concerns they may have in regard to the study and/or consent process. Under HIPAA waiver, the study team will identify potential subjects from clinic schedules, OR schedules and Maestro Care.

8. Subject's Capacity to Give Legally Effective Consent:

Patients who do not have the capacity to give legally effective consent will not be approached for participation in this study.

9. Study Interventions:

See 4 above.

10. Risk/Benefit Assessment:

Patients will not incur any added risk to standard risks incurred with regional anesthesia. These standards risks are:

- Regional anesthesia - minor pain or discomfort, injury to arteries, veins or nerves affecting the arms or legs, residual numbness or weakness or paralysis, headache, muscle soreness, infection, allergy or adverse drug reaction, intravascular injection of local anesthetic causing seizure or cardiac arrest.

Patients will be monitored in the post-operative care unit by nurses assigned to their care. Once pain scores ≥ 5 , the study team will be notified and the intervention will be performed. Patients will have post-operative analgesics available for pain control that include 25mcg IV fentanyl for pain scores 5-7 and 50mcg IV fentanyl for pain scores 8-10. Fentanyl will not be administered prior to intervention unless intervention cannot be performed within 5 minutes of notification by PACU nurse.

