Benefits include contributing to general knowledge base to improve future patient care. This includes potential confirmation of analgesic benefit, decreased pain scores, and improved patient satisfaction. Conversely, this study may show no benefit of the block, thereby invalidating the technique.

11. Costs to the Subject:

Subjects will not incur any additional costs to participate in the study. A MaestroCare build will be created to ensure that any subjects are not charged for researched related procedures, equipment, or medications.

12. Data Analysis & Statistical Considerations:

The primary hypothesis, that there is a difference in numeric pain score at 4 hours postoperatively between the intervention groups, will be assessed with a two-sided 2 group t-test or Mann-Whitney-Wilcoxon test as appropriate. We will perform a secondary repeated measures ANOVA or non-parametric Friedman test to assess difference in numeric pain score over the full 24-hour period. If there is evidence of a difference in numeric pain score during the 24-hour period, we will perform post-hoc pair-wise multiple comparison corrected tests to identify the time-points where the intervention groups differ on pain score. Additional secondary analyses will assess differences in cumulative opioid consumption in IV morphine equivalents and motor strength for both tibial and common peroneal nerves with parametric or non-parametric tests as appropriate. Statisticians employed by the Department of Anesthesiology will conduct these analyses.

A total of 40 participants will be enrolled in the study, randomized equally between study (n=20) and placebo (n=20) groups based on sample size calculation for a non-parametric Mann-Whitney Test with $\alpha=0.05$, $\beta=0.8$, difference in means=2, and effect size of 1.0. The sample size required for a non-parametric test will provide greater than 80% power if the data meet requirements for a parametric t-test.

13. Data & Safety Monitoring:

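### 20 per arm reproduces, but 40 consented is equated with 40 randomised with no allowance for patients who never reach the PACU pain trigger, and their numbering and scoring are undefined

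*Combined protocol and SAP*

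**What the plan says.** **Size.** Section 12: "A total of 40 participants will be enrolled in the study, randomized equally between study (n=20) and placebo (n=20) groups". The calculation is for a Mann-Whitney test with α=0.05, a difference of 2 points and an effect size of 1.0. It prints β=0.8, and the next sentence begins: "The sample size required for a non-parametric test will provide greater than 80% power" (on the condition that the t-test applies).

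**Who the 40 are.** Section 6: "A total of 40 patients will be consented from Duke University Medical Center". Section 5 fixes the moment: "written informed consent will be obtained on the day of surgery prior to receiving any sedation". Section 4 has the allocation made "prior to any patient enrollment. Patients will be given a number (1-40"), without saying when a given patient receives a number.

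**The gate.** Block or sham is given only after a pain score in recovery reaches the trigger. Sections 4 and 10 put this at 5 or more; Section 2 puts it above 5. Section 2 describes a general anaesthetic, Section 4 a spinal.

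**Analysis set.** Section 2 states intent to treat. Nothing is said about a patient who never reaches the trigger.

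**Clock.** Section 12's primary hypothesis is that "there is a difference in numeric pain score at 4 hours postoperatively between the intervention groups". Section 4 starts scoring elsewhere: "At the completion of the intervention, verbally reported pain scores (NRS 11"), with that point as time zero.

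**The concern.** Consented, enrolled and randomised are all 40, although a post-consent event decides who is treated. If some patients never reach the trigger, the plan leaves open whether they have been randomised. If they have, they belong in the intent-to-treat comparison, where they carry no treatment effect and dilute the difference. If they are dropped, the arms fall below 20. The two routes give different power, and without a rule the choice could be made after the data are seen.

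The two clocks add to this. For a treated patient they pick out different scores. If the block were completed one hour after surgery (an assumed gap), the score at 4 hours after surgery would fall 4 − 1 = 3 hours after the block. For a never-blocked patient, the Section 4 clock never starts.

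**Working it through.** **Inputs from the documents.** Two-sided α=0.05 (Sections 2 and 12); difference 2 and effect size d=1.0 (Section 12), so the implied SD is 2/1.0 = 2; 20 per arm; power 80%.

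**Step 1: reproduce N.**
- t-test (noncentral t): 16.7 per arm, so 17.
- Mann-Whitney, t-test n divided by the asymptotic relative efficiency (ARE): 16.7/0.955 = 17.5, so 18 (normal data); 16.7/0.864 = 19.3, so 20 (minimum ARE).
- Noether: p = Φ(1/√2) = 0.760; N = (1.960 + 0.842)² / [12 × 0.25 × (p − 0.5)²] = 38.6 in total, so 20 per arm.

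The plan's 20 per arm is confirmed. With all 40 analysed, power is 81.4% (Noether or minimum ARE), 85.3% (normal-data ARE) or 86.9% (t-test).

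**Step 2: β.** Read literally, β=0.8 means 20% power, which needs 3.6 per arm, so 4. The sentence about 80% power and the N of 20 both show that power 0.8 (β=0.2) was meant. No result changes.

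**Step 3: never-blocked patients.** The non-trigger rate f is not in the documents, so every value below is an assumption. Simulation: 40,000 trials per cell (standard error about 0.2 points); integer scores 0–10; sham mean 5, block mean 3, SD 2; number not triggering binomial in each arm. *Kept* patients have mean 3 and SD 2 in both arms, assuming a 4-hour score is obtained. Mann-Whitney is tie-corrected; ranges are with and without continuity correction.

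| f | Mann-Whitney, kept | Mann-Whitney, excluded | t-test, kept | t-test, excluded |
|---|---|---|---|---|
| 0% | 84–85% | 84–85% | 86% | 86% |
| 5% | 80% | 82–83% | 82% | 84% |
| 10% | 74–75% | 80% | 76% | 82% |
| 20% | 63–64% | 74–75% | 66% | 77% |
| 30% | 51–52% | 68–69% | 54% | 71% |

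The kept rows follow from dilution: the target difference becomes 2 × (1 − f), that is 1.9, 1.8, 1.6 and 1.4 points at 5, 10, 20 and 30%.

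**Checks.**
- Excluded, analytic with n = 20 × (1 − f) = 19, 18, 16 and 14 per arm: normal-data ARE 83.3, 81.2, 76.1 and 70.0%; Noether 79.4, 77.2, 72.2 and 66.5%.
- Kept, with continuous scores and never-blocked patients scoring like sham patients (20,000 trials): 81, 75, 64 and 52% at 5, 10, 20 and 30%.
- Kept, with the never-blocked mean set to 2 or 4 instead of 3: 79, 73, 60 and 46%, or 80, 75, 64 and 53%.

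**Step 4: consents needed for 40 randomised at the trigger.** 40/(1 − f), rounded up: 43, 45 and 50 at 5, 10 and 20%, so 3, 5 and 10 extra.

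**The case against.** **The wording may be loose.** Section 12 speaks of 40 randomised 20:20 and Section 4 numbers patients 1–40, so consented in Section 6 may simply mean randomised. If numbers were given at the trigger and recruitment ran to 40, no power would be lost. This stands as a possible reading, but the text does not settle it, and Section 6 as written caps consents at 40.

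**Intent to treat is stated.** This also stands: a numbered patient stays in the assigned arm. What is missing is narrower, namely when the number is assigned and how a numbered patient without an intervention is scored.

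**Stronger readings that the documents do not support.**
- A reader might infer that 80% power holds only if essentially all 40 reach the trigger. The Noether calculation that yields exactly 20 does give 79.4% at 19 per arm, and at f = 5% the chance that all 40 trigger is 0.95⁴⁰ = 13%. But the simulated Mann-Whitney power is still about 80% at 5% kept or 10% excluded, so a few such patients are tolerable.
- A reader might infer that a never-blocked patient has no scheduled score. That is true only on Section 4's completion-of-intervention clock. On Section 12's postoperative clock a score could exist, and Section 4's later sentence on hourly recording names no anchor.
- A reader might take β=0.8 as a sizing error. It is clerical.

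**The rate is unknown.** The loss is conditional on a figure the documents do not give. Nor can it be inferred while the trigger and the anaesthetic are each stated in two ways.

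**Conclusion.** The sample size is sound; the definition of who fills it is not. The plan equates 40 consented before sedation with 40 randomised despite a later pain gate, and leaves numbering and scoring undefined for patients who do not pass it.

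Any shortfall is conditional. Mann-Whitney power remains about 80% up to roughly 5% non-trigger (kept) or 10% (excluded). It is about 75% at 10% kept or 20% excluded, and about 64% at 20% kept. These figures assume d=1.0, SD 2, no effect in never-blocked patients and equal non-trigger rates in the two arms.

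The double timing of the primary score is a defect whatever the trigger rate. The point should be fixed before analysis, but it does not invalidate the design.

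**What to change.** 1. **Sections 4, 6 and 12:** assign the next number (1–40) only when the patient reaches the trigger, and state that 40 is the number randomised. The allocation list can still be prepared beforehand. Cost: about 3, 5 or 10 extra consents at assumed non-trigger rates of 5, 10 or 20%. There are also a few more injections than under 40 consented: at 10%, 40 against 40 × 0.9 = 36. The unblinded team member must be promptly available at the trigger, since Section 10 allows fentanyl first if the intervention cannot be performed within 5 minutes. If 40 consented is kept instead, state the power as conditional on the trigger rate and say how never-blocked patients are scored and analysed.
2. **Sections 4 and 12:** state one time anchor for the 4-hour primary score, and say what it is for a numbered patient whose injection is not completed. Cost: wording.
3. **Sections 2, 4 and 10:** reconcile the two trigger statements and the general and spinal anaesthetic statements. No choice between them is made here.
4. **Section 12:** adjust the primary comparison for the pain score already taken at the trigger (ANCOVA or its rank version). Cost: one degree of freedom. The gain is probably modest: the equivalent size is 20/(1 − r²), or 20.8, 22.0 and 26.7 per arm at assumed correlations of 0.2, 0.3 and 0.5. Because only scores at or above the trigger enter, the lower values are more plausible.
5. **Section 12:** replace β=0.8 with power=0.8 (β=0.2). Cost: none.
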